3.4 Study Population

3.4.1 Use of Vulnerable Populations

This study focuses on adults experiencing moderate or high CVD risk and homelessness (CVH). This is justified given the premature morbidity and mortality of this population. While not formally considered a vulnerable population, CVH are a population requiring special attention regarding safety and respectful engagement in research.

A consent quiz will be used to ensure that no individuals unable to consent are recruited similar to protocols used in [name] other studies.

Furthermore, we will continue working closely with staff at Catholic Charities, other community partners, and a multi-stakeholder team to ensure we achieve cultural congruence with the ways we approach and engage this population in research as well as with the planned study protocols.

3.5 Inclusion and Exclusion Criteria

3.5.1 Inclusion Criteria

Inclusion criteria:

1. Age 18 yrs. or older
2. English-speaking
3. Have experienced homelessness or housing insecurity in the past 2 years
4. Self-reported diagnosis of moderate or high CVD risk, defined as being told by a medical professional that the participant has hypertension, hypercholesterolemia, prediabetes, type 2 diabetes, or heart disease
5. Plan to stay in local area or be reachable by phone for the next 16 weeks
6. Willingness to work on one or more CVD risk reduction behavior change identified during the screener. The behavior change meet specified qualifying criteria for each CVD risk behavior (below; also see Assessment table for exact wording of screening questions). (i.e., If the patient uses combustible tobacco products, they qualify and must be willing to work on quitting tobacco. If the participant qualifies for the study because they get less than 6 hours of sleep per night. They must be willing to work on getting more sleep as the focus of coaching.)
 - a. Quitting tobacco: Any use of combustible tobacco in the last 30 days
 - b. Taking prescription medications: Having daily prescriptions and reporting missed doses some, most, or every time they were due in the last 7 days; or wanting help getting prescription medications (e.g. medications advised in the past but not currently receiving).
 - c. Getting healthy sleep: Sleeping <6 hours or >9 hours per night
 - d. Moving your body: <3 days per week with 30 minutes or more of moderate physical activity
 - e. Eating healthy: <5 days per week following healthful eating plan, getting 5 or more servings of fruits and vegetables, or >2 days per week eating high fat foods.

3.5.2 Exclusion Criteria

1. Active intoxication
2. Active psychosis
3. Presence of a legal guardian
4. Pregnant or lactating people

Patients who do not meet all enrollment criteria will not be enrolled. Any violations of these criteria will be reported in accordance with IRB Policies and Procedures.

Rationale for excluding pregnant people: People who are pregnant may have less control over their health and typically receive guidelines from their provider on diet and exercise during pregnancy. Though we do not think participation in this study poses a risk to pregnant people, we do not think we can accurately measure the effect of our program in this population.

Retain participants who become pregnant during the study:

Risk of withdrawing care: We have opted to retain participants who become pregnant after enrollment because a) we do not think interaction with a wellness coach poses greater than minimal risk and b) prematurely withdrawing the care of the wellness coach from a vulnerable population (pregnant people who are experiencing homelessness) poses a greater risk than continued participation.

Mitigation of risk: Our coaching is designed to adapt to the unique goals of each participant, and we recognize that people who become pregnant during the study will likely be working on their cardiovascular health with their care team. In the case that a participant becomes pregnant, we will ask the participant to sign a release of information so we can communicate with their OB, midwife, or other provider overseeing their pregnancy to ensure coaching goals align with the diet and wellness goals established by the provider.

4 STUDY PROCEDURES

4.1 Qualifying Visit

4.1.1 Eligibility, screening visit

As outlined in Table 1, before consent, interested participants will complete a phone or in-person screening. This will cover inclusion and exclusion criteria and briefly describe the intervention to ensure the participant is aware and willing to commit to study.

4.1.2 Baseline Assessment

The baseline assessment will begin with the participant's signed consent. As outlined in Table 1 above, the screening visit and baseline assessment visits will collect:

- Informed Consent, HIPPA authorization
- Review Inclusion/Exclusion Criteria
- Demographics/Medical History
- Release of information for health systems used in last 12 mo.
- Primary care team
- Biometric data including height, weight, blood pressure, skin carotenoids, hemoglobin A1c, and cholesterol levels.
 - Fingerstick (1-3 drops; collected by study staff) will be collected, run on point-of-care machines (e.g. Cholestech, DCA Vantage, A1C Now, CardioChek Plus), and then disposed of appropriately following the biometrics protocol for CV-Homes. In case of machine malfunction, venous blood samples (100 microliters) will be scheduled for study participants and collected at HCH or Hennepin Healthcare labs.
 - Skin carotenoids will be measured using reflection spectroscopy by a non-invasive machine called the VEGGIE METER. As confirmed via email, the VEGGIE METER is a patented and validated piece of technology that has been used in NIH- funded research. There is a standard protocol for use which will be followed.
- Patient-reported outcome survey items and physiological measures: See Table 2

After consent and HIPPA authorization are obtained, study staff will access participants' medical records to confirm a diagnosis of one of the qualifying CVD risk conditions. If patients are found not to qualify at this point, they will be excluded from the study.

Table 2. Measurement and classification of Life's Essential 8 composite measure of CV health.¹⁸

LE8 Item	Measure	Scoring
Physical Activity	Measurement: Self-reported minutes of moderate or vigorous PA per week NHANES PAQ-K questionnaire	Metric: Minutes of moderate- (or greater) intensity activity per week Scoring: Points Minutes 100 ≥ 150 90 120–149 80 90–119 60 60–89 40 30–59 20 1–29 0 0
Diet	Measurement: Self-reported daily intake of a DASH-style eating pattern; MEPA	Quantiles of DASH-style diet adherence: Points MEPA score (points) 100 15–16 80 12–14 50 8–11 25 4–7 0 0–3
Nicotine Exposure	Measurement: Self-reported use of cigarettes or inhaled NDS; NHANES SMQ	Metric: Combustible tobacco use or inhaled NDS use; or secondhand smoke exposure Scoring: Points Status 100 Never smoker 75 Former smoker, quit ≥ 5 y 50 Former smoker, quit 1–<5 y 25 Former smoker, quit <1 y, or currently using inhaled NDS 0 Current smoker Subtract 20 points (unless score is 0) for living with active indoor smoker in home; NHANES seems to define current as 30 days
Sleep health	Measurement: Self-reported average hours of sleep per night Example tools for measurement: “On average, how many hours of sleep do you get per night?”	Metric: Average hours of sleep per night Scoring: Points Level 100 7–<9 90 9–<10 70 6–<7 40 5–<6 or ≥ 10 20 4–<5 0 <4 Consider subtracting 20 pts if untreated or undertreated sleep apnea
Weight	BMI (weight [kg]/height [meters] squared on scales, stadiometers)	Metric: BMI (kg/m ²) Scoring: Points Level

		
  
100	<25	
 
70	25.0–29.9	
 
30	30.0–34.9	
 
15	35.0–39.9	
 
0	≥40.0	
  
 
Clinicians may want to assign 100 points for overweight individuals (BMI, 25.0–29.9 kg/m²) who are lean with higher muscle mass.
	100	<25	70	25.0–29.9	30	30.0–34.9	15	35.0–39.9	0	≥40.0						
100	<25																	
70	25.0–29.9																	
30	30.0–34.9																	
15	35.0–39.9																	
0	≥40.0																	
Blood pressure	Resting systolic and diastolic BP via standard measurement	
Metric: Systolic and diastolic BPs (mm Hg)
 
Scoring:
 
  
Points	Level	
   
100	<120/<80 (optimal)	
 
75	120–129/<80 (elevated)	
 
50	130–139 or 80–89 (stage 1 hypertension)	
 
25	140–159 or 90–99	
 
0	≥160 or ≥100	
  
 
Subtract 20 points if treated level
	Points	Level	100	<120/<80 (optimal)	75	120–129/<80 (elevated)	50	130–139 or 80–89 (stage 1 hypertension)	25	140–159 or 90–99	0	≥160 or ≥100				
Points	Level																	
100	<120/<80 (optimal)																	
75	120–129/<80 (elevated)																	
50	130–139 or 80–89 (stage 1 hypertension)																	
25	140–159 or 90–99																	
0	≥160 or ≥100																	
Blood glucose	Blood analyzed via point of care/lab testing	
Metric: HbA1c (%)
 
Scoring:
 
  
Points	Level	
   
100	No history of diabetes and HbA1c <5.7	
 
60	No diabetes and HbA1c 5.7–6.4 (prediabetes)	
 
40	Diabetes with HbA1c <7.0	
 
30	Diabetes with HbA1c 7.0–7.9	
 
20	Diabetes with HbA1c 8.0–8.9	
 
10	Diabetes with Hb A1c 9.0–9.9	
 
0	Diabetes with HbA1c ≥10.0	
  
	Points	Level	100	No history of diabetes and HbA1c <5.7	60	No diabetes and HbA1c 5.7–6.4 (prediabetes)	40	Diabetes with HbA1c <7.0	30	Diabetes with HbA1c 7.0–7.9	20	Diabetes with HbA1c 8.0–8.9	10	Diabetes with Hb A1c 9.0–9.9	0	Diabetes with HbA1c ≥10.0
Points	Level																	
100	No history of diabetes and HbA1c <5.7																	
60	No diabetes and HbA1c 5.7–6.4 (prediabetes)																	
40	Diabetes with HbA1c <7.0																	
30	Diabetes with HbA1c 7.0–7.9																	
20	Diabetes with HbA1c 8.0–8.9																	
10	Diabetes with Hb A1c 9.0–9.9																	
0	Diabetes with HbA1c ≥10.0																	
Total cholesterol	Blood analyzed via point of care/lab testing	
Metric: Non-HDL cholesterol (mg/dL)
 
Scoring:
 
  
Points	Level	
   
100	<130	
 
60	130–159	
 
40	160–189	
 
20	190–219	
 
0	≥220	
  
 
If drug-treated level, subtract 20 points
	Points	Level	100	<130	60	130–159	40	160–189	20	190–219	0	≥220				
Points	Level																	
100	<130																	
60	130–159																	
40	160–189																	
20	190–219																	
0	≥220																	
LE8 Total Score	Average of all 8 category scores (100-80 high CVH; 79-50 moderate CVH; 49-0 Low CVH)																	

Since a goal of this treatment development trial is to refine both the flow of the initial baseline assessment visits as well as which patient-reported instruments are best tolerated, not all participants will receive all survey items. Informed consent and HIPAA authorization will always be collected at baseline assessment visit 1. However, we will adjust when other data are collected based on participant and assessment surveyor feedback.

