Statistical And Analytic Plan	
The primary endpoint of this study is the feasibility and acceptability of the program to participants in this treatment development phase. We will summarize themes in the end-of treatment interview, assess satisfaction via structured survey, and assess treatment dose received via frequency, length, and type of communications with study staff.
 
We will conduct exploratory analyses on our eventual primary behavioral endpoint of cardiovascular health. We will refine our use of patient-reported outcomes for use in a future randomized pilot trial.

Data And Safety Monitoring Plan	
[name] (PI) will work closely with study staff to monitor the quality of data collected at assessment. This treatment development study (N=8), does not meet NIH criteria requiring a Data Safety Monitoring Board (DSMB), however [name] will oversee a detailed safety monitoring plan.

TABLE 1: SCHEDULE OF STUDY PROCEDURES

Study Phase	Eligibility screening	Consent, Baseline assessment	Treatment sessions										Follow-up visit
			1	2	3	4	5	6	7	8	9	10	
Visit Number			1	2	3	4	5	6	7	8	9	10	
Study Weeks	0	1	2-3	4	5	6	7	8	9	10	11	12	13-16
Confirm communication preferences	X	X	X				X						X
Review Inclusion/Exclusion Criteria	X	X											
Informed Consent		X											
Demographics/Medical History, experiences of discrimination		X											
Vital Signs: BP, HR		X											X
Height and Weight		X											X
Point of care LDL and blood glucose		X											X
Skin Carotenoids		X											X
Medication review		X											X
Self-report survey measures		X											X
Satisfaction with intervention													X

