1.1 Introduction

The overall goal of this project is to expand our team's existing evidence-informed programs to specifically target multiple health behavior change to decrease the cardiovascular (CV) health risk of people experiencing homelessness in Minnesota and beyond. This is relevant to health disparities given the disproportionate number of Black, Indigenous, and other people of color (BIPOC) who are homeless. We plan a sequential exploratory mixed methods study design for treatment development familiar to our team from prior work (K23DK118117) with ongoing input from our community-engaged research team (Fig 2).

Aim 2. Assess the feasibility and acceptability of CV-HOMES for people who have experienced homelessness in a single arm treatment development trial (n=8). We hypothesize feasibility (e.g., recruitment, treatment engagement, retention) and acceptability (of study procedures and CV-HOMES treatment). This will include examining changes in the American Heart Association's Life's Essential 8 score as our targeted clinical outcome.

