3.3.2 Total Number of Study Sites/Total Number of Participants Projected

Enrollment for the study will continue until 8 participants have been recruited or when enough data has been gathered to inform future steps of treatment development.

HHRI will serve as the only site for this study. Catholic Charities offers space in the community for study related activities to minimize burden on participants. The study team will connect with other housing and community partners to identify community spaces if necessary.

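### Table 2 stops the 20-point deduction at 0 for nicotine but not for blood pressure, non-HDL cholesterol or sleep, so an item can score -20 on a 0-100 scale (minor)

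*Combined protocol and SAP*

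**What the plan says.** Table 2 scores each of the eight LE8 items from 100 points down to 0. Four rows then carry a 20-point deduction:

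- Blood pressure: "Subtract 20 points if treated level". The lowest band, systolic ≥160 or diastolic ≥100 mm Hg, is worth 0 before the deduction.
- Total cholesterol (scored on non-HDL): "If drug-treated level, subtract 20 points". The lowest band, ≥220 mg/dL, is worth 0.
- Sleep: "Consider subtracting 20 pts if untreated or undertreated sleep apnea". The lowest band, under 4 hours, is worth 0.
- Nicotine: "Subtract 20 points (unless score is 0) for living with active indoor smoker in home". Only this row exempts a score of 0.

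The total is given as "Average of all 8 category scores (100-80 high CVH; 79-50 moderate CVH; 49-0 Low CVH"), so its categories end at 0. No section says how a negative item would be handled.

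Section 1.1 says of Aim 2: "This will include examining changes in the American Heart Association's Life's Essential 8 score as our targeted clinical outcome". The synopsis gives the status of that analysis: "We will conduct exploratory analyses on our eventual primary behavioral endpoint of cardiovascular health". The primary endpoint is feasibility and acceptability (section 6.1).

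**The concern.** The same table protects the bottom of the scale in one row and leaves it open in three. Followed literally, it produces item values that the 0-100 scale has no place for. An analyst who reads the nicotine exception as the general intention would stop at 0; one who follows each row as printed would not. The two would get different baseline scores and, for some participants, different changes from the same measurements.

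The cells can be reached. Section 3.5.1 admits people with diagnosed hypertension or high cholesterol, and missed doses of prescribed medicines are one of the qualifying behaviours. Section 8.4 sets blood pressure alerts at levels inside the lowest band. Section 1.3 plans to carry the efficacy measures into a randomised pilot and then a larger trial, so an unsettled scoring rule would go with them.

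**Working it through.** **Inputs (Table 2).** Band points, best to worst: blood pressure 100, 75, 50, 25, 0; non-HDL 100, 60, 40, 20, 0; sleep 100, 90, 70, 40, 20, 0; nicotine 100, 75, 50, 25, 0. The deduction is 20. Total = sum of 8 items / 8. Planned sample: 8 (section 3.3.2).

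**Reproducing the stated range.** The total-score row implies 0 to 100.

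- As written, item = points - 20. Treated blood pressure scores 80, 55, 30, 5, -20. Treated non-HDL scores 80, 40, 20, 0, -20. Sleep with the apnea deduction scores 80, 70, 50, 20, 0, -20. Minimum total = (-20 - 20)/8 = -5, or (-20 - 20 - 20)/8 = -7.5 with sleep. The stated range is not reproduced.
- With a floor, item = max(0, points - 20). Only the lowest band changes, from -20 to 0. The minimum total is 0 and the stated range is reproduced.

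**Size per person and per group.** One affected item: 20/8 = 2.5 LE8 points. Blood pressure and cholesterol together: 40/8 = 5. One affected item in one of 8 people: 2.5/8 = 0.3125 on the group mean.

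**When the total itself goes negative.** With one item at -20, the other seven must sum to less than 20. With two, the other six must sum to less than 40. Off-scale values are therefore mainly an item-level matter.

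**Effect on change.** The two rules give different changes only when a person is in the lowest band with the deduction applied at one visit but not at the other.

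| Scenario | Item change as written | Item change with floor | LE8 as written / with floor |
|---|---|---|---|
| BP, treated at both visits, ≥160 to 140-159 | -20 to 5 = +25 | 0 to 5 = +5 | +3.1 / +0.6 |
| BP, treated at both visits, 140-159 to ≥160 | 5 to -20 = -25 | 5 to 0 = -5 | -3.1 / -0.6 |
| BP, untreated at both visits, ≥160 to 140-159 | 0 to 25 = +25 | +25 | +3.1 / +3.1 |
| BP, treatment starts, stays ≥160 | 0 to -20 = -20 | 0 to 0 = 0 | -2.5 / 0 |
| BP, treatment starts, stays 140-159 | 25 to 5 = -20 | -20 | -2.5 / -2.5 |
| Non-HDL, treated at both visits, ≥220 to 190-219 | -20 to 0 = +20 | 0 to 0 = 0 | +2.5 / 0 |

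Rows 1 and 3 show that, with treatment constant, the deduction cancels and the literal rule gives the same change as in an untreated person. It is the floor that shrinks the change. Row 4 is the case where the missing floor alone creates an apparent worsening. Row 5 shows that a 20-point drop on starting treatment also occurs in a higher band under either rule, so that drop belongs to the deduction and not to the floor.

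**The case against.** A reader might infer that the missing floor distorts change in general, or inflates improvement in people treated at both visits. The arithmetic does not support that. Their +25 matches the change in an untreated person, the literal rule enlarges worsening as much as improvement relative to the floor, and no directional bias follows. A reader might also infer that LE8 totals will often fall below 0; that would need nearly every other item to be near 0.

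The rest of the opposing case is about consequence. LE8 is exploratory, section 5.2 says efficacy is not the aim, and section 6.2.2 attaches no test or decision rule to LE8. Section 6.1 keeps the biometric and self-report data in REDCap, so scores can be recalculated. The documents give no rate of treated participants in the lowest bands. Table 2 also reproduces a cited published instrument, and whether that source sets a floor cannot be checked from the documents.

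All of this stands, and it limits the severity. It does not remove the inconsistency: within one table, one row exempts a score of 0, three do not, and the three as printed yield values below the stated scale.

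**Conclusion.** The point holds as a minor scoring inconsistency. As written, a treated participant at ≥160 or ≥100 mm Hg, a treated participant with non-HDL ≥220, or an under-4-hour sleeper given the optional apnea deduction scores -20 on that item. The cost is 2.5 LE8 points per affected item per person. For a participant who starts treatment and stays in the lowest band, the missing floor alone produces a false LE8 fall of 2.5. For those treated at both visits, the result depends on an unsettled choice of rule, and neither rule is shown to be the unbiased one.

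This assumes that Table 2 is applied literally and that no scoring code outside the documents already imposes a floor. The group figure of 0.31 assumes 8 people with both assessments. Enrolment may end on another criterion ("Enrollment for the study will continue until 8 participants have been recruited or when enough data has been gathered"); with fewer people the shift per affected person is 2.5/n and so larger. How often the lowest treated bands will occur is unknown.

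**What to change.** In Table 2, add to the deductions in the blood pressure, total cholesterol and sleep rows the exemption for a score of 0 that the nicotine row already has. That wording is enough, because no non-zero band in those rows falls below 0 after the deduction (blood pressure 25 to 5, non-HDL 20 to 0, sleep 20 to 0). State that every item is scored within 0-100 and that the same rule is used at baseline and at the final assessment.

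The cost is a few words in the table and a limit in whatever code computes the score. The downside is real: the floor compresses change for treated participants who move into or out of the lowest band, and a treated move from non-HDL ≥220 to 190-219 would show no change at all. Reporting the measured blood pressure and non-HDL values beside the scores would keep such moves visible.

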Key Criteria for Inclusion and Exclusion:	(1) Moderate to high CV risk defined as self-reported diagnoses by a medical professional of high blood pressure, high cholesterol, prediabetes, type 2 diabetes, or heart disease. (2) Experience of homelessness per the HEARTH Act which includes living in a supported housing facility (2011). (3) English-speaking, (4) and willingness to engage in coaching about changes to ≥1 health behavior related to cardiac risk that align with patients' personal CV risk behaviors. Medical diagnoses and medications will be confirmed in medical records after enrollment.
	Patient exclusion criteria will include conditions raising risk for coercion or limitation of capacity to ethically consent to research: (1) active intoxication, (2) active psychosis or dementia, (3) active legal commitment (per search of publicly available civil court records) or (4) pregnancy or lactation. This is aligned with previous studies by this team (K23DK118117).
	We will further confirm capacity to consent using a brief quiz (see attachments).
Number Of Participants	Total Number of Participants: 8

	
Total Number at Hennepin Healthcare: 8
 
Total Number of Sites: 1

Study Duration	
Each participant will be enrolled for 16 weeks.
 
The entire study is expected to last one year.

Study Phases	(1) Screening : screening for eligibility and obtaining consent, baseline assessment
Screening	(2) Intervention : study intervention with counselor support approximately weekly in-person and/or by phone x 12 weeks
Intervention	
Follow-Up	(3) Follow-up : final assessment
Efficacy Evaluations	
 • Cardiovascular health as measured by the American Heart Association's Life's Essential 8 score.¹⁸ This includes: 
 ○ Self-reported cardiovascular health behaviors (eating better, being more active, taking medications as prescribed, quitting tobacco, getting healthy sleep) ○ Blood pressure and body mass index (height, weight) ○ Cholesterol and Hemoglobin A1c measured by point-of-care fingerstick or venous blood draw ○ Skin carotenoid measurement by VEGGIE METER • Self-reported medication adherence • Self-reported psychological wellness • Self-reported drug and alcohol use • Self-reported health care use
Safety Evaluations	Not applicable in this single arm trial

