3.1.1 Screening Phase and Baseline Assessment

Recruitment protocols are summarized in section 9.5. Screening will be conducted by phone or in-person as requested by participants. It will focus on ensuring they meet inclusion criteria and assessing current health behaviors to inform which behaviors might be targeted by wellness coaches. Baseline assessment will consist of informed consent, self-reported survey items, and biometric data including cholesterol, A1c, and skin carotenoid measurement via VEGGIE METER. Blood samples for cholesterol and A1c will be collected by fingerstick and measured on the DCA Vantage, Cholestech, A1c Now Professional, or CardioChek Plus Analyzer (1-3 drops of blood). If the POC machines using small amounts of blood are malfunctioning, venous blood draws (100 microliters) may be scheduled and collected for the study at the Healthcare for the Homeless or

Hennepin Healthcare labs. Participants will be informed of results in lab letter after appointment (2023.12.21 CV-Homes.LabLetter).

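### Table 1 schedules LDL, but the Life's Essential 8 lipid item is scored on non-HDL cholesterol, and HDL is not listed for collection

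*Combined protocol and SAP*

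**What the plan says.** Table 1 (schedule of study procedures, in the synopsis) has a single laboratory line, "Point of care LDL and blood glucose", marked at the baseline assessment and at the follow-up visit.

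Table 2 in Section 4.1.2 defines LE8. Its lipid row carries the label "Total cholesterol" and describes the measurement only as "Blood analyzed via point of care/lab testing". The scoring cell begins "Metric: Non-HDL cholesterol (mg/dL" and gives five bands: below 130 scores 100, 130–159 scores 60, 160–189 scores 40, 190–219 scores 20, and 220 or more scores 0. The total is the "Average of all 8 category scores".

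Elsewhere the fraction is not specified. The synopsis has "Cholesterol and Hemoglobin A1c measured by point-of-care fingerstick or venous blood draw", Section 3.1.1 has "Blood samples for cholesterol and A1c will be collected by fingerstick", and the Section 4.1.2 list has "hemoglobin A1c, and cholesterol levels". HDL appears only inside the term non-HDL.

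LE8 is the targeted clinical outcome (Sections 1.1 and 6.1). The primary endpoint is feasibility and acceptability (Section 6.1), and the synopsis calls the cardiovascular health analyses exploratory. The synopsis also makes the feasibility of measuring cardiovascular risk at two time points a primary objective.

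**The concern.** The schedule and the scoring table name different lipids. LDL alone does not yield non-HDL. A site that collects exactly what Table 1 lists does not have the input that Table 2 needs.

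Two things could follow. The lipid item could be missing, and the document gives no rule for forming an eight-item average when one item is absent. Or the LDL value could be entered against cut-points meant for non-HDL. That gives a plausible score and leaves no visible sign of the error.

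This bears on the stated objective of showing that cardiovascular risk can be measured at two visits. Section 1.3 also says that the efficacy measures are intended for a later randomized pilot and a larger trial, so an uncorrected schedule could be carried forward.

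**Working it through.** The plan gives no figure to reproduce here. The check compares the two tables and then applies the Table 2 bands to assumed lipid values.

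**Inputs from the document.** The Table 2 bands listed above, and the item's weight of 1/8 in the LE8 total.

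**Assumed inputs (not in the document).** Total cholesterol (TC) from 140 to 280 mg/dL in steps of 20; HDL 30, 40, 50, 60 or 70; triglycerides (TG) 100, 150 or 200. Participants are taken as not drug-treated, so the 20-point deduction does not apply.

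**Formulas.**
- Non-HDL = TC − HDL.
- LDL = TC − HDL − TG/5 (assumed estimating formula).
- Error in the LE8 total = (item score using LDL − item score using non-HDL) / 8.

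**If LDL is scored on the non-HDL bands**

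| TC / HDL / TG | Non-HDL (score) | LDL (score) | Error in LE8 total |
|---|---|---|---|
| 160 / 50 / 150 | 110 (100) | 80 (100) | (100 − 100)/8 = 0 |
| 220 / 50 / 150 | 170 (40) | 140 (60) | (60 − 40)/8 = +2.5 |
| 200 / 50 / 150 | 150 (60) | 120 (100) | (100 − 60)/8 = +5.0 |
| 200 / 40 / 200 | 160 (40) | 120 (100) | (100 − 40)/8 = +7.5 |

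The grid has 8 × 5 × 3 = 120 combinations. One is dropped because its LDL falls below 40 (140 / 70 / 200 gives 30), leaving 119. Across these the error runs from 0 to +7.5. It is non-zero in 76 of 119 (about 64%) and zero in 43 (about 36%). These shares describe the grid, not a patient population. The error is never negative, because under this formula LDL never exceeds non-HDL.

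**Effect on change, with LDL used at both visits.** The error need not cancel.
- From 200/50/150 to 160/50/150, the correct change is (100 − 60)/8 = +5.0; with LDL it is (100 − 100)/8 = 0.
- From 220/50/150 to 200/50/150, the correct change is (60 − 40)/8 = +2.5; with LDL it is (100 − 60)/8 = +5.0.

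So change can be understated or overstated.

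**If the item is missing and the other seven are averaged.** Let m be the mean of the other seven items and c the unseen lipid score. The shift in the total is m − (7m + c)/8 = (m − c)/8. For an assumed m = 60, this is (60 − 0)/8 = +7.5 when c = 0 and (60 − 100)/8 = −5.0 when c = 100.

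**The case against.** The best defence is that the Table 1 line is shorthand. The same line says blood glucose, while Table 2 and the procedure text use HbA1c. Section 4.1.2 speaks of cholesterol levels in the plural and refers to a separate biometrics protocol. Other sections refer to an Assessment Table. Neither is reproduced here, and Section 6.1 says that all biometric data go into REDCap. If the device derives LDL from total cholesterol and HDL, both components already exist and non-HDL follows at once. This stands as far as it goes: the document does not show that HDL is unavailable. It does not remove the conflict, because Section 4.1.2 itself points to Table 1 for what the screening and baseline visits collect.

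A reader might go further and infer that three rival lipids are named, so that total cholesterol could be scored by mistake. The document supports this only weakly. The first column of Table 2 names domains, as with weight (scored on BMI) and blood glucose (scored on HbA1c), and the metric beside the lipid label is unambiguous.

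A reader might also infer that a different lipid could be recorded at each visit and mimic change. Table 1 marks the same line at both visits, and nothing in the document suggests a switch.

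Finally, the stakes are limited. Section 5.2 says that efficacy is not the aim, the sample is eight people, Section 6.2.2 specifies no LE8 test, and the item is one eighth of the score.

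**Conclusion.** The inconsistency is real and sits in a table meant to direct data collection: Table 1 schedules LDL, Table 2 needs total cholesterol and HDL, and HDL is not listed for collection. If only LDL is recorded, the lipid item cannot be scored. If LDL is scored on the non-HDL bands, the LE8 total is biased upward by 0 to about 7.5 points. That range rests on the assumed lipid grid and the assumed LDL formula, and some profiles show no error.

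It would be tempting to conclude that the item will be lost, or that every participant would be misclassified. The document supports neither. It does not say what the analyzers report, and the biometrics protocol may already specify a panel that includes HDL. Because LE8 is a secondary, exploratory outcome here, the importance is modest. The correction is still worth making before data are collected, since a component that was never recorded may not be recoverable in a sample of eight.

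**What to change.** - Change the lipid entry in Table 1 to total cholesterol and HDL, with non-HDL computed.
- Confirm that the analyzers and the biometrics protocol deliver both components, that REDCap has a field for each at both visits, and that non-HDL is computed there as total cholesterol minus HDL.
- As a minor accompanying edit, relabel the Table 2 row non-HDL cholesterol.
- State in a sentence how the LE8 total is formed if the lipid item is missing.

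The cost is a few wording changes and at most two REDCap fields per visit, provided the devices in use report HDL, which needs to be confirmed. If a panel with HDL is already run, the edits only document current practice.
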